Date: Tuesday, January 28, 2020 1:45:11 PM

Print

Close

IRB_00086498

Created: 9/19/2015 4:57 PM

PI: [name]

Submitted: 3/29/2016

Title: Spectacle Tints and Thin-Films to Reduce Headache Frequency
in Patients with Migraine

1. Study Introduction

1. Responsible Investigator:

[name]

Email	Training	Col Date
[contact]	4/11/2019 MCG	1/16/2020

a. Position of the Investigator:

 Faculty or Non-Academic Equivalent Student Staff Resident/Fellow Other

2. Contact Persons for the Responsible Investigator:

Name	Email	Training
[name]	[contact]	3/31/2018 MCG
[name]	[contact]	G
[name]	[contact]	2/10/2017 MC
[name]	[contact]	3/3/2017 MCG
[name]	[contact]	1/28/2020 MG

3. Guests of the Responsible Investigator:

Last Name	First Name	E-Mail
[name]	[name]	[contact]

4. What type of application is being submitted?

New Study Application (or Amendment/Continuing Review)

5. Title Of Study:

Spectacle Tints and Thin-Films to Reduce Headache Frequency
in Patients with Migraine

6. Study Purposes and Objectives:

Previous research has shown that both spectacle tints and spectacle thin-films can be an effective treatment in migraine. The purpose of this study is to determine if one of these treatments, tints or thin-films, is superior to the other.

7. Is this a multi-site study, where more than one site needs IRB approval? Yes No**8. Background and Introduction:***Brief Description*

Nearly all migraine sufferers report sensitivity to light during a headache and a significant proportion of sufferers report light sensitivity between attacks. Light is also a common trigger for migraine headaches. Spectacle lenses that have been treated with tints and spectacle lenses that have been treated with thin-films have both been shown to reduce light sensitivity and headache in patients with migraine. At this time, it is not clear which spectacle lens treatment is superior. The purpose of this trial is to determine if there's a significant, therapeutic advantage to either spectacle lens treatment. Both treatments could be a novel, non-invasive adjuvant in the treatment of migraine.

Detailed description

Approximately 6% of men and 18% of women are afflicted with migraines. (Stovner et al., 2006) Over 90% of patients with migraines report a sensitivity to light (photophobia) during headaches. (Evans et al., 2008) Some migraine sufferers report that light can trigger a migraine and some have a chronic sensitivity to light (Main et al., 1997). Migraineurs are especially sensitive to non-incandescent lighting sources such as fluorescent lights, computer monitors, and gas-vapor lamps ([name] and Digre, 2016).

The pathway that mediates photophobia appears to involve intrinsically photosensitive retinal ganglion cells ("IPRGs"; Hattar et al., 2002) and trigeminal afferents (Nosedá et al., 2010; Digre and Brennan, 2012). These retinal cells do not require input from photoreceptors to be activated by light, and they have been shown to be responsible for circadian rhythm entrainment and the pupillary light reflex. As such, these cells constitute a pathway separate from that of the visual pathway (Güler et al., 2008). IPRGs contain the chromophore melanopsin. In these cells, 480 nm light (in the blue-green portion of the visible spectrum) isomerizes melanopsin and triggers the phototransduction cascade. However, IPRGs can also be stimulated by rods and cones. Thus, IPRGs can be stimulated *directly* by 480-nm light or *indirectly* by any light in the visible spectrum.

In the present study, we will use a neutral gray tint to decrease stimulation of the eye by all wavelengths in the visible spectrum. We will compare this intervention to a thin-film spectacle coating designed to specifically block 480-nm light. The gray tint will decrease both direct and indirect stimulation of the IPRGs by blocking all wavelengths of the visible spectrum. The 480-nm thin-film will specifically target direct stimulation of the IPRG.

All tints and thin films will be calibrated such that the optical density, that is the overall "darkness" of all study lenses, will be the same. All study lenses will appear to have the same overall light blocking effect to study subjects. The lenses are intended to be a preventative or prophylactic treatment for migraine.

IRB_00086498

Created: 9/19/2015 4:57 PM

PI: [name]

Submitted: 3/29/2016

Title: Spectacle Tints and Thin-Films to Reduce Headache Frequency
in Patients with Migraine

2. Study Location and Sponsors

2. Specific age range of participants (e.g., 7-12 years old, 60+, etc.):

between ages of 18 and 80 inclusive

3. Indicate any vulnerable participant groups (other than children) included:

None

If "Other", please specify:

If "None" and no children are involved, answer the following question.

Has the participant selection process overprotected potential subjects who are considered vulnerable so that they are denied opportunities to participate in research?

Yes No

4. Number of participants to be included and/or enrolled in this entire study, across all study locations: 140

At Utah prior to October 2019: 20

5. Characteristics of Participants/Inclusion Criteria:

For inclusion, subjects must meet the International Headache Society criteria for chronic migraine (International Classification of Headache Disorders, 3rd edition (Headache Classification Committee of the International Headache Society, 2013; Figure 1A) - OR - subjects must meet the International Headache Society criteria for episodic migraine (Headache Classification Committee of the International Headache Society, 2013; Figure 1B) AND have at least 8 headache days per month ("high-frequency episodic migraine"). All subjects must be between the ages of 18 and 80 years-old.

To be included in the study, in the best judgment of the investigator, subjects must be stable on their current migraine treatment regimen. Stability is defined as no major changes in therapy contemplated within the next 4 months.

Subjects should be on a stable course of all prescription medications for the 4 weeks preceding enrollment.

6. Participant Exclusion Criteria:

Subjects with other light sensitive conditions, such as iritis and blepharospasm, will be excluded. Subjects with best-corrected visual acuity less than 20/40 will be excluded. Subjects with diseases of the retina, such as diabetic retinopathy and macular degeneration will be excluded. Subjects using medications known to affect the eye will be excluded (e.g. chloroquine, hydroxychloroquine, ethambutol, amiodarone). Due to constraints on the manufacture and mounting of study lenses into study frames, the study must exclude subjects who are very nearsighted (more than 4 diopters), subjects who are very farsighted (more than 2 diopters), and subjects who have more than 2.5 diopters of astigmatism.

Because of the cyclical effects of botulinum toxin injections and other nerve blocks, patients undergoing these treatments will be excluded. Subjects must not have had any injections or blocks within 4 months of enrollment and should not receive any further blocks until they exit the study.

Subjects with *continuous daily* headache (a headache frequency of 100%) will be excluded. Subjects who do not have a headache frequency of at least 8 days per month will be excluded.

Subjects with medication overuse headache will be excluded (Figure 1C). A patient with a history of medication overuse who has not overused abortive medications for the past 4 months can be included.

Subjects who abuse alcohol or use illicit drugs will be excluded.

Subjects may continue to use their customary preventative, abortive or rescue medications for migraine throughout the trial.

7. Is a substantial percentage of the participant population anticipated to be non-English speaking?

Yes No

IRB_00086498

Created: 9/19/2015 4:57 PM

PI: [name]

Submitted: 3/29/2016

Title: Spectacle Tints and Thin-Films to Reduce Headache Frequency
in Patients with Migraine

4. Study Information

1. Design of Study (select all that apply):

Prospective Clinical Research
Randomized
Other

If Other, describe:

Active control

2. Does your study involve the use of any placebo?

Yes No

3. Length of entire study, from initiation through closeout:

30 months

4. How will participants be recruited or identified for inclusion in the study?

a. Select all methods that will be used:

In-person contact (e.g., patients, students, etc.)

Referrals

Written advertising (flyers, brochures, website postings, newspaper ads, etc.)

From a database or participant pool for which participants have given prior permission to be contacted for research studies

Other

A website has been created for recruitment purposes. This website has been optimized such that internet search engines looking for information about migraine or light sensitivity will be able to identify the site. www.migraineglassesstudy.com.

A 45-second recruitment video has been developed to aid recruitment and is embedded in the website.

The website has a questionnaire embedded that potential participants may complete. This questionnaire will help potential participants determine if they meet the inclusion and exclusion criteria; the completed questionnaire will be forwarded to the clinical coordinator at the site closest to the potential participant.

This study can also be found by individuals searching the ClinicalTrials.gov website.

b. Describe the recruitment/participant identification process in detail (e.g. who will review charts or records, who can refer participants to the study, where will flyers be posted, how often will recruitment letters be sent, when will follow-up phone calls be made, etc.):

Physicians treating patients for migraine will ask potential subjects if they might be interested in participating in the research. If patients agree, they will be contacted by a study coordinator who will give them additional information about the study and determine eligibility. If still interested, subjects will be invited to participate.

A recruitment letter may be sent to patients who have been seen in the University's headache clinic.

The recruitment video will be posted on the Moran Eye Center's Facebook page and "blasted" to Facebook subscribers who live near any of the study sites and who have mentioned "headache", "migraine", or "light sensitivity" on their Facebook page.

5. How will consent be obtained?

Informed Consent Process (with or without a document)

6. **Describe all the procedures chronologically, from screening/enrollment through study closeout, which will be completed in the research project.**

Each subject will be randomized to receive spectacles treated with either a thin-film coating or a conventional tint. The conventional tint will serve as an “active control”. In an effort to keep subjects masked to the intervention to which they’ve been assigned, subjects will be told that both tints and thin films have been shown to improve headaches and that the purpose of the study is to determine if thin films or tints are more effective. Subjects will not be informed that there is a “control”, “placebo” or “sham” intervention.

Subjects will be told that the lenses are to be used to reduce the frequency and severity of headaches and their impact on daily activities. Accordingly, during the intervention period, subjects will be instructed to wear their spectacles during all waking hours.

Subjects who do not wear glasses will be given study spectacles without any optical correction. Subjects who already wear glasses will be given customized spectacles that incorporate their optical correction. Subjects who customarily wear contact lenses will be asked to wear glasses without an optical correction over their contact lenses.

The optical properties of the thin film coating and the gray tint are shown in Figure 2. All spectacles will have the same overall optical density across the visible spectrum. This statement means that all study eyewear will appear to have the same amount of “darkness” to the subject. The total study duration will be 16 weeks

Table 1. Protocol Visit Schedule

Visit	Week	Activities
1	0	Determine eligibility
		Informed Consent
		HIT-6
		Baseline photophobia and ADL questionnaire
		Receive diary
		Randomization
2	4	Diary check
		HIT-6
		Receive glasses/Check glasses fit
3	8	Diary check
		HIT-6
		Check glasses fit

4	12	Diary check
		HIT-6
		Check glasses fit
5	16	Diary check
		HIT-6
		Final photophobia, ADL and masking questionnaires
		Keep glasses OR receive compensation and return glasses

Baseline Visit 1 (Week 0)

Subjects who meet study inclusion and exclusion criteria will be invited to participate in the study. Potential subjects will have all of their questions about the study answered. Subjects who agree to participate will sign an informed consent document and be given a copy of the document. They will fill out a baseline questionnaire regarding light sensitivity and activities of daily living (Figure 3). They will complete the 6-item Headache Impact Test (HIT-6; Figure 4) The HIT-6 is copyrighted, but its use is not restricted by the holder of the copyright and it's not necessary to get permission or pay the copyright holder for use of the questionnaire. At the discretion of the site PI or coordinator, this visit may be completed by phone. Study materials including the informed consent document and questionnaires may be transmitted by U.S. mail, email, or fax.

Subjects will be randomized with equal allocation to receive either tinted or thin-film coated spectacles. A random permuted block randomization will be employed. However, before receiving their study spectacles, subjects will complete a four-week "baseline period" during which no study lenses will be worn. This period will help establish the base-line characteristics of their headaches. Subjects will keep daily diaries throughout the 16-week study detailing the frequency and severity of their headaches (Figure 5).

Visit 2 (Week 4)

When subjects return after the 4-week baseline period, the research team will review their diaries. Subjects must provide at least 20 days of diary data and must have had at least 15 headache days (defined as a calendar day consisting of at least 4 hours of continuous headache). This requirement helps insure subjects meet the definition of chronic migraine. Subjects must have had at least 4 distinct headache episodes each lasting at least 4 hours during the 4-week baseline period. This requirement helps insure that subjects with continuous headache are not included in the study, as these subjects are often unresponsive to any headache treatments. Subjects whose diaries do not meet these criteria will exit the study. Subjects whose diaries indicate that they are overusing abortive pain medications will exit the study. Subjects who exit the study at this point will be given a \$25 gift card. At the discretion of the site PI or coordinator, this visit may be completed via phone. Study instruments including the diaries and questionnaires may be completed by phone or transmitted by U.S. mail, email or fax. Alternatively, these instruments may also be completed by the participant within REDCap.

Subjects whose diaries meet these criteria will complete a questionnaire and receive their study spectacles. The research team will insure the glasses fit comfortably and will instruct the subjects to wear them full time. Subjects will receive new diaries.

Visit 3 (Week 8)

The research team will review the subject's diaries, insure the subject's glasses still fit comfortably, and will instruct the subject to continue to wear the glasses full-time. Subjects will complete a questionnaire and receive new diaries. At the discretion of the site PI or coordinator, this visit may be completed via phone. Study instruments

including the diaries and questionnaires may be completed by phone or transmitted by U.S. mail, email or fax. Alternatively, these instruments may also be completed by the participant within REDCap.

Visit 4 (Week 12)

The research team will review the subject's diaries, insure the subject's glasses still fit comfortably, and will instruct the subject to continue to wear the glasses full-time. Subjects will complete a questionnaire and receive new diaries. At the discretion of the site PI or coordinator, this visit may be completed via phone. Study instruments including the diaries and questionnaires may be completed by phone or transmitted by U.S. mail, email or fax. Alternatively, these instruments may also be completed by the participant within REDCap.

Visit 5 (Week 16)

At the final visit, subjects will turn in their diaries. Subjects may elect to keep their study glasses or receive a \$100 gift card. Subjects will complete a final light sensitivity and activities of daily living questionnaire (Figure 6) and a masking questionnaire required by FDA (Figure 7). For long-term follow-up, subjects will be asked if they may be contacted at 6 and 12 months after the completion of the follow-up period to determine if they are still using the study lenses. At the discretion of the site PI or coordinator, this visit may be completed via phone. Study instruments including the diaries and questionnaires may be completed by phone or transmitted by U.S. mail, email or fax. Alternatively, these instruments may also be completed by the participant within REDCap.

Study coordinators will contact subjects by telephone once between each study visit to insure they are completing their diaries and wearing their study-related spectacles. These weekly contacts will also enable coordinators to identify and address any barriers to adherence with the protocol. These contacts will help maximize retention and minimize loss to follow-up. The Week 8 and Week 12 visits are intended to help with subject retention and to insure subjects are completing their diaries.

7. Are all procedures for research purposes only (non-standard or non-standard of care procedures)?

Yes No

If no, list the procedures that are performed for research purposes only (non-standard or non-standard of care procedures):

8. Is there a safety monitoring plan for this study?

Yes No

9. Provide a summary of the statistical methods, data analysis, or data interpretation planned for this study. Factors for determining the proposed sample size (e.g., power) should be stated.

Preliminary Analyses

Baseline characteristics will be summarized by randomized treatment group with standardized differences between treatment groups used to assess the balance of patient characteristics between the two groups. Univariate summaries will also be performed at baseline and follow-up for the primary and secondary outcome variables. If quantitative outcome variables exhibit substantial skewness, transformations may be sought to better approximate normality.

Primary Analysis of Headache Days

The primary analysis of the efficacy of the thin-film intervention will be conducted as an analysis of covariance comparing the proportion of days during the 12 week follow-up period recorded as headache days between the thin-film treatment group and the tinted glasses group, using the proportion of headache days during the 4-week baseline as a covariate. The null hypothesis of no treatment effect on headache frequency will be rejected if the 2-sided p-value corresponding to the treatment effect is smaller than 0.05.

In a secondary analysis, generalized estimating equations (GEE) will be applied to a generalized linear model in which the probability of reporting a headache day during the treatment period is related to a) the baseline frequency of headache days, b) the randomized treatment group, c) week of follow-up, defined as a categorical variable, and d) the interaction of the randomized treatment group with follow-up week. This analysis will be used to characterize the treatment effect over different portions of the follow-up period. A binary outcome model with a logistic link function will be used. A compound symmetry working covariance matrix will be applied and robust standard errors will be used for statistical inferences. The analysis will provide estimates of the odds ratio (with associated 95% confidence intervals and p-values) for reporting a headache day between the two treatment groups obtained separately for each follow-up month. If the interaction between the randomized treatment group and week of follow-up is not statistically significant at the $\alpha=0.05$ level, an overall estimate of the odds ratio for reporting a day with severe headache between the two treatment groups will be provided under a reduced model which excludes the randomized treatment group by follow-up week interaction. For reporting purposes, we will

also provide ratios of the probabilities for reporting headache days using a marginal means approach, with bootstrap resampling used to estimate 95% confidence intervals and p-values.

Analysis of HIT-6

The main secondary analysis of the HIT-6 Total Score will be performed using a linear mixed effects model for a normally distributed outcome. The mixed effects model will relate the mean HIT-6 scores at weeks 4, 8, 12, and 16 of treatment to a) the baseline (week 0) HIT-6 score, b) the randomized treatment group, c) the follow-up visit, defined as a categorical variable, and d) the interaction of the randomized treatment group with follow-up visit. An unstructured covariance model will be used to account for repeat observations over the three follow-up assessments. The main contrast to evaluate the treatment effect will compare the mean HIT-6 scores over the 4, 8, 12 and 16 week visits; additional exploratory contrasts will compare the HIT-6 scores at weeks 4, 8, 12, and 16 individually.

Sample Size and Power

In a subgroup of 22 subjects with at least 50% and less than 100% headache days in our pilot crossover trial, the pooled mean \pm standard deviation for the follow-up % of headache days across the two periods was 69.0% \pm 18.6%. We observed a Pearson correlation of 0.55 between the baseline and follow-up % of headache days. Assuming the same means and standard deviations, and allowing for 10% loss-to-follow-up, 140 randomized subjects (70 for each treatment group) will provide 80% power with 2-sided $\alpha=0.05$ to detect a mean reduction in the % of headache days of 7.8%. This would represent, for example, a decrease from 69.0% headache days to 61.2% headache days.

The effect size of 7.8% is under half the assumed follow-up standard deviation of 18.6% points, and thus represents a moderate effect size.

Other Secondary Outcomes

To measure severity of headaches, we will use the subjects' daily diaries to count the number of days with headache that either a) made activity difficult, b) caused activity changes, or c) caused patient to go to bed. We will compare the proportion of days that are free of headaches leading to any one of these three criteria using the same GEE approach that was described for the sensitivity analysis of the frequency of headache days.

Exploratory Outcomes

- a. Proportion of subjects who were able to move out of the "very severe impact" category of the HIT-6 between baseline and the three follow-up assessments.
- b. Proportion of patients who experienced at least a 5-point improvement in their HIT-6 score from baseline to each of the three follow-up assessments (weeks 8, 12, and 16).
- c. Proportion of days that are free of headaches that require use of medications to control the headache over the 12-week intervention.
- d. Proportion of days with light sensitivity over the 12-week intervention.
- e. Average Number of Hours Slept per night over the 12-week intervention.

Subject participants ages 18-22 years ("transitional adolescents")

We are interested in the comparative effectiveness of tints and coatings in the treatment of migraine within this age group. Enrollment and randomization will be stratified within this age group to allow a statistical analysis for this subgroup. Subjects in this age group will have a separate block randomization. Based on previous experience, we anticipate enrolling 6-8 subjects in this age group.

Analysis Plan for Secondary and Exploratory Outcomes

Outcomes defined as proportions of days meeting designated criteria based on diary information. Analyses of secondary and exploratory outcomes defined by proportions of days during the follow-up period that satisfy designated conditions will be carried out using the same GEE approach that was described for the secondary analysis of the proportion of headache-free days. Thus, for each outcome, we will estimate the treatment effect separately during each of the four follow-up months as well as the overall effect across all 4 follow-up months.

Numeric outcomes. Descriptive summaries and graphical displays using histograms will provide numeric outcome variables at baseline and over the respective follow-up assessments, by treatment group. Transformations may be sought to better approximate normality for outcomes exhibiting substantial skewness. Numeric secondary and exploratory outcomes that are assessed at baseline and the week 4, week 8, week 12 and week 16 follow-up visits will be analyzed using the linear mixed effects modeling approach described for the HIT-6 score.

Multiple comparisons. Both the primary and the main secondary outcomes will be compared between the randomized groups using a 2-sided α -level of 0.05. Additional secondary and exploratory outcomes will also be compared between the treatment groups using a 2-sided α level of 0.05, without adjustment for multiple comparisons. However, all results from these analyses will be interpreted as exploratory and will take into account the risk of Type 1 errors resulting from multiple hypothesis tests.

Missing Data. The computation of the % of headache days will include only those days with non-missing headache diary information. This analysis will remain approximately unbiased as long as the days on which headache status is recorded in the diaries are independent of actual headache status. The analysis of the HIT-6, which is based on a linear mixed effects model, will be approximately unbiased so long as the pattern of missing data is missing at random, meaning that the probability that an outcome measurement is missing may depend on the values of other non-missing measurements, but not on the value of the missing measurement itself. If the fraction of missing HIT-6 scores exceeds 10% at any given follow-up visit, multiple imputation will also be applied prior to the analysis of the main secondary HIT-6 outcome.

Interim Analysis.

No formal interim analyses for efficacy will be performed.

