2. Describe the plan to control, store, and dispense the investigational device. This plan should ensure that the device is only used by qualified investigator(s) for the participants enrolled in this research project.

The following label will be affixed to the inside of case for the glasses:

Axon Optics, LLC, Salt Lake City, UT, USA

CAUTION: Investigational device. Limited by Federal law to investigational use. Not suitable for night driving.

Thin film coatings for spectacles are similar in design to anti-reflective coatings commonly dispensed for prescription and cosmetic eyewear. Anti-reflective coatings may be purchased without a prescription. There are no known risks to subjects from anti-reflective or other thin-film coatings. In a previous study of thin-film coatings and migraine, there were no adverse effects of the coatings. The tinted spectacles used in this study will be similar to non-prescription eyewear one could purchase without a prescription. However, because the study lenses are part of an investigational medical device study, all spectacle frames that contain study lenses will be numbered and stored in a locked cabinet. Only the research team at each site will have access to lenses and the research team will use an Excel log to track the location of all study lenses.

IRB_00086498**Created:** 9/19/2015 4:57 PM**PI:** [name]**Submitted:** 3/29/2016**Title:** Spectacle Tints and Thin-Films to Reduce Headache Frequency in Patients with Migraine

Non-Significant Risk Device

Review the following definition of a non-significant risk (NSR) device:

1. The medical device is not a significant risk device, because all of the following are true:
 - a. The medical device is NOT intended as an implant that presents a potential for serious risk to the health, safety, or welfare of a subject.
 - b. The medical device is NOT purported or represented to be for a use in supporting or sustaining human life that presents a potential for serious risk to the health, safety, or welfare of a subject.
 - c. The medical device is NOT for a use of substantial importance in diagnosing, curing, mitigating, or treating disease, or otherwise preventing impairment of human health that presents a potential for serious risk to the health, safety, or welfare of a subject.
 - d. The medical device is does NOT otherwise present a potential for serious risk to the health, safety, or welfare of a subject.
2. The medical device is not banned.

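### Subjects are told to wear the study spectacles whenever awake, with no night-driving exception, although the device label warns against night driving and the risk section omits the hazard

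*Combined protocol and SAP*

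**What the plan says.** Section 4, item 6, sets the wear rule for the intervention period: "subjects will be instructed to wear their spectacles during all waking hours". When the glasses are dispensed at Visit 2 (Week 4), the research team "will instruct the subjects to wear them full time". At Visit 3 (Week 8) and again at Visit 4 (Week 12), the team "will instruct the subject to continue to wear the glasses full-time". No exception is attached to any of these.

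The section on investigational use of a device, item 2, introduces the device caution with "The following label will be affixed to the inside of case for the glasses". The caution includes "Limited by Federal law to investigational use. Not suitable for night driving". In the text available, this is the only mention of night driving.

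Section 6, item 1, names three risks: discomfort from glasses in people not used to them, no improvement in headache, and a breach of confidentiality. It otherwise expects no significant risk.

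Item 6 also defines three lens groups. For the first, "Subjects who already wear glasses will be given customized spectacles that incorporate their optical correction". For the second, "Subjects who customarily wear contact lenses will be asked to wear glasses without an optical correction over their contact lenses". People who wear neither glasses nor contact lenses get study glasses with no correction.

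**The concern.** Driving at night is a waking activity, so the wear rule in item 6 covers it while the sponsor's own label advises against it. The plan leaves the subject to settle the contradiction, and its other provisions favour wear. Coordinators telephone between visits to check that the glasses are being worn and to deal with obstacles to adherence. Under the Safety Monitoring Plan, item 4a, an investigator may withdraw a subject for not complying. Nothing says that taking the glasses off to drive at night counts as compliant.

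What is at stake is participant safety. All study lenses have the same overall optical density, so both arms are affected. Subjects may also choose at Visit 5 to keep the glasses, so clear advice is useful beyond Week 16.

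**Working it through.** The point rests on comparing texts. The arithmetic only describes how widely the instruction applies.

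**Texts side by side**

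| Place | Content | Night-driving exception? |
|---|---|---|
| Section 4, item 6 | Wear whenever awake | None |
| Visit 2 (Week 4) | Wear full time | None |
| Visits 3 and 4 (Weeks 8 and 12) | Continue full-time wear | None |
| Device section, item 2 (case label) | Not for night driving | This is the caution itself |
| Section 6, item 1 (risks) | Three risks listed | Hazard not listed |

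The direct contradiction is between the first row and the label. The visit instructions, given three times, repeat the rule without resolving it.

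**Plan's own sample size, reproduced first.** Inputs from Sample Size and Power (Section 4, item 9): SD 18.6, baseline correlation 0.55, difference 7.8 points, two-sided α 0.05, power 80%, loss 10%.

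- Residual SD after covariate adjustment: 18.6 × √(1 − 0.55²) = 15.53.
- Per arm: n = 2 × (1.960 + 0.842)² × 15.53² / 7.8² ≈ 62.3, rounded up to 63.
- After 10% loss: 63 / 0.90 = 70 per arm, 140 in total.

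The stated 140 reproduces. Power with 63 per arm is 80.5%. A night-driving exception changes none of these inputs.

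**Reach of the instruction**

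- Wear period: Week 4 to Week 16 = 12 weeks × 7 = 84 days.
- Subjects: randomization takes place at Visit 1, but glasses go only to those who pass the Week 4 diary check. If the 10% allowance covers every loss, 140 × 0.90 = 126 complete, so between 126 and 140 receive glasses.
- If Week 4 exits come on top of that allowance, the number may be below 126. The plan gives no exit rate.

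These figures count subjects and days under the instruction. They do not count night drives or expected events.

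**What an exception must cover.** Eligibility allows up to 4 diopters of nearsightedness, 2 of farsightedness and 2.5 of astigmatism. A subject whose study lenses carry the prescription would be driving uncorrected if told only to take them off. Subjects whose study glasses have no correction, including contact-lens wearers, lose nothing by removing them.

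**The case against.** The strongest reply is that the plan already carries the warning. The label comes with the glasses, and a general wear rule can be read together with a specific caution: wear them all day except in the one use the device advises against. No text tells anyone to drive at night in the lenses. This is a fair reading, but the plan does not adopt it. The caution is inside a case, while the contrary instruction is given by staff at three visits and backed by adherence calls and possible withdrawal.

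Second, the consent document is not in the text reviewed and may warn subjects. That stands as a limit: it is not known whether subjects are under-warned. A consent warning would still leave the staff instructions and the risk list at odds with the label.

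Third, the hazard is not sized. The lens properties are in Figure 2, which is not available here. The device section reports no adverse effects of the coatings in an earlier study and likens the tinted glasses to eyewear sold without prescription. This also stands, and it is why no event rate is given. The sponsor nevertheless chose this caution for this trial's glasses.

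Fourth, the figures of 84 days and 126 to 140 subjects do not measure night driving. That is correct, and they are not offered as such.

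Finally, people who already wear glasses would ordinarily still have their own pair, so the risk of driving uncorrected does not come from the current plan. That is accepted. It bears on how the exception is worded.

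**Conclusion.** The concern holds. The wear rule conflicts with the sponsor's device caution, and the risk section leaves the hazard out. The rule applies for 84 days, is reinforced at three visits, and reaches 126 to 140 subjects if the 10% allowance covers all losses, possibly fewer otherwise.

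The conclusion takes the label at its word that the lenses are unsuitable for night driving. It does not depend on the lens density or on the content of the consent document. It is a safety and disclosure point only: the primary comparison, the type I error and the power are untouched. It should be corrected because the rule, followed as written, puts night drivers in both arms into the use the label warns against.

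**What to change.** In Section 4, item 6, and in the Visit 2, 3 and 4 instructions, require wear during waking hours except when driving at night, and say what each group does:

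- Subjects whose study lenses carry their prescription change to their own untinted glasses. Staff can confirm at Visit 2 that they have such a pair.
- Subjects with uncorrected study glasses take them off. Contact-lens wearers keep their contacts in.

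Add reduced vision when driving at night to Section 6, item 1, and confirm that the consent document agrees. Optionally, state in the Safety Monitoring Plan, item 4a, that this removal is not non-compliance.

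The cost is a short exception and one line of risk text, with no added visits or procedures. Subjects who drive at night will have slightly less wear time, under the same rule in both arms.
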